5.4 Internal pilot trial

The pilot will build on previous research in this participant group undertaken by team members [6, 30, 41], which has already provided information on trial administration, the characteristics of sciatica participants and the effects of biological treatments from previous studies [42]. The internal pilot will rehearse the procedures and logistics to be undertaken in the main trial. It will assess the feasibility of the arrangements for delivering the interventions, recruitment rate and initial retention rate. The internal pilot will be based on the first 50 participants recruited into the trial. We plan to start recruitment in two centres (including North Wales and London) and then to roll out recruitment in the other three centres over the next three months. We expect the recruitment rate to build over the first three months up to the target rate of four participants per collaborating centre per month. We anticipate that this will take seven months. The indicative stopping criteria at the end of this internal pilot will be recruitment which fails to reach 80% of the planned recruitment rate target, drop outs up until the six week postal questionnaire assessment exceeding 20%, or more than one centre failing to commence recruiting. Mindful of the problem of inappropriate

stopping of a trial if the reasons for the delay are identified and solved the Data Management and Ethical Committee (DMEC) will then make recommendations to the Trial Steering Committee (TSC), and the HTA manager for discussion and decision on stopping the trial. Any procedural changes identified in the pilot would be implemented across all trial sites subject to ethical approval of the appropriate major amendment. Data from participants in the internal pilot will be automatically rolled into the main trial data unless the trial management group believe that data to be incompatible with the remaining data [40]. No interim analysis at the primary endpoint (one year) is proposed and therefore this internal pilot will not affect the overall power of the trial. Wittes and Brittain's [42] method will be used for sample size recalculation if required. More details in how to implement this will be pre-specified in the statistical analysis plan (SAP), which will be approved by the TSC before the start of any data analysis.

Data collection

	STUDY PERIOD					Follow up period		
	Enrolment	Randomisatio n (within 2-3 weeks of registration)	Treatment Visit 1 (within 3 days of randomisation)	Treatment Visit 2	6 week	6 month	12 month	
Time point:								
Eligibility	Х	Х						
Informed Consent	X	X						
Registration to Trial	X							
FBC	Х							
Urine pregnancy test U&E's	X X							
TB Screening	X							
MRI	Х							
MRI reporting*	Х*						X*	
Eligibility confirmed	X	X						
Randomisation		Х						
Subcutaneous Injection of allocated treatment			X	X				
Physiotherapy Treatment				X	X			
ODI		Х			Х	Х	Х	
EQ-5D-5L		Х			Х	Х	Х	
RMDQ		Х			Х	Х	Х	
SBI		Х			Х	Х	Х	
STarT Back Tool		Х						
PSEQ		Х			Х	Х	Х	
HADS		Х			Х	X	Х	
TSK		Х			Х	Х	Х	
RUQ		Х			Х	X	Х	
Pain Outcome		Х			Х	Х	Х	
Manikin pain diagram		X			X	X	X	
Pain Duration		X						
Pain Trajectory		X			V		V	
Days of work		Х			X	X	X	
Global Assessment of change					X	X	X	
Adverse Events		Х	Х	Х	Х	X		

*The findings of the MRI will only be available to the participants treating clinician after completion of the study. Individual results will be made available if a report is needed in an emergency, or if a spinal surgery referral is being contemplated and will be shared with the clinical team, referring GP and the musculoskeletal clinician

6. Primary outcome

The primary clinical outcome will be back pain specific disability measured using the Oswestry Disability Index [32] at 12 months. The primary economic outcomes will be the incremental cost per QALY gained, estimated by administering the EQ-5D-5L at each follow-up visit.

6.1 Outcome measures

6.1.1 Condition specific outcomes

• Back pain specific disability using the Oswestry Disability Index [32]

The Oswestry Disability Index is an outcome assessment tool that is used to measure a participant's impairment and quality of life (i.e., how badly the pain has affected their life). The participant questionnaire contains topics concerning intensity of pain, lifting, ability to care for oneself, ability to walk, ability to sit, sexual function, ability to stand, social life, sleep quality, and ability to travel. Each topic category is followed by six statements describing different potential scenarios in the participant's life relating to the topic. The participant then checks the statement which most closely resembles their situation. Each question is scored on a scale of 0-5 with the first statement being zero and indicating the least amount of disability and the last statement is scored 5 indicating most severe disability. The index is scored from 0 to 100. Zero is equated with no disability and 100 being maximum disability. It will be used at the first clinical assessment to assess eligibility and also at the second clinical assessment to confirm eligibility. If recruited onto the trial this will be used as the baseline measurement. It will also be measured at follow-up after six weeks, six and twelve months.

• Leg pain related functional disability using the leg pain version of the Roland– Morris Disability Questionnaire [43, 44]

The Roland-Morris Disability Questionnaire (RMDQ) is a measure of disability where greater levels of disability are reflected by higher numbers on a 24-point scale. The RMDQ is a self-administered outcome measure. Participants are asked to read the list of 24 sentences and placing a tick against appropriate questions based on how they feel each sentence describes them today. If the sentence does not describe their symptoms today, participants are asked to leave the space next to the sentence blank. Participants are asked to tick next to the sentence if they are sure it describes them today. The RMDQ is scored by adding up the number of items checked by the participant. The score can therefore vary from 0 to 24. If participant indicate in any way that an item is not applicable to them, the item is scored 'No', i.e. the

denominator remains 24.It will be measured at baseline, six weeks, six and twelve months follow-up.

• Leg pain interference using the Sciatica Bothersomeness Index (SBI) [45]. This is an index based on participants reporting of symptoms which reflects the trouble the participant is going through with his/her sciatica symptoms. The index includes self-reported ratings of symptom intensity of: leg pain; numbness or tingling in the leg, foot or groin; weakness in the leg/foot; back or leg pain while sitting. Each symptom item is rated on a scale from 0 to 6, with 0 being not bothersome, 3 somewhat bothersome and 6 extremely bothersome. It will be measured at baseline, six weeks, six and twelve months follow-up.

• Pain location using a pain manikin [46]. This is a picture of a human figure (manikin) on which pain is indicated by the participant and can be used to measure musculoskeletal pain.

It will be measured at baseline, six weeks, six and twelve months follow-up.

6.1.2 Generic outcomes

• Health utility using EQ-5D-5L [33].

This is a participant completed index of health related quality of life, which gives a weight to different health states. It consists of five dimensions: mobility, self-care, usual activities, pain/discomfort, and anxiety/depression. Each has five levels of severity (no problems/some /moderate problems / extreme problems and unable to). It will be used at baseline, six weeks, six and twelve months follow-up. It allows the calculation of quality adjusted life years (QALYs), using area under the curve method which will be used as part of the economic analysis.

• Global assessment of change since baseline

The global assessment of change is a measure of changes in levels of pain over a set time period. It will be measured at six weeks, six and twelve months follow-up.

6.1.3 Psychological outcomes

 Anxiety and depression using the Hospital Anxiety and Depression Scale (HADS) [47].

This is a participant completed outcome measure of anxiety and depression. It is designed to measure anxiety and depression in participants with physical health problems. It has seven items related to common symptoms of anxiety and 7 for depression. Participants are asked whether they experience the symptom definitely,

sometimes, not much or not at all. The HADS was designed for use in the hospital setting but has been used successfully with the general population. It will be used at baseline, six weeks, six and twelve months follow-up.

6.1.4 Use of health care and social care services

• Resource Use Questionnaire (RUQ) [48, 49].

This is used for collecting retrospective information about trial participants' use of health and social care services, out of pocket expenses and lost earnings. It will be administered at baseline, six weeks, six and twelve months follow-up.

6.1.5 Employment

• Questions on employment status, work absence, sick certification and selfcertification.

These will be used at baseline, six weeks, six and twelve months follow-up.

6.1.6 Process Measures (potential predictors and mediators of outcome)

Risk of poor outcome using the

• STarT back screening tool [50].

This screening tool assesses patients' risk of persistent disabling pain. Patients risk subgroup (low, medium or high risk) has been shown by team members to be predictive of outcomes, including patients with back pain and with suspected sciatica. This will be measured at baseline only.

• Pain trajectory based on a single question [51].

This question is used to classify low back pain duration and asks "How long is it since you had a whole month without any back pain?" There are seven discrete response categories:- Less than three months, three to six months, seven to twelve months, one to two years, three to five years, six to ten years and more than ten years. This shows that recalled duration of pain is a predictor of outcome in low back pain patients, independent of baseline severity and psychological status.

• Pain self-efficacy questionnaire (PSEQ) [52].

The PSEQ is a 10-item questionnaire, developed to assess the confidence people with ongoing pain have in performing activities while in pain. The PSEQ is applicable to all persisting pain presentation. It covers a range of functions, including household chores, socialising, work, as well as coping with pain without medication. It will be used at baseline, six weeks, six and twelve months follow-up.

• Fear avoidance beliefs using the Tampa Scale of Kinesiophobia [53]
The TSK is a 17-item checklist that is used to measure the fear of movement (re)injury related to chronic back pain. The scale is based on the model of fear avoidance, fear of work related activities, and fear of movement/re-injury. It will be used at baseline, six weeks, six and twelve months follow-up.

6.2 Follow up

The guestionnaires will follow best practice in their design to maximise response rate, participants will receive alerts prior to questionnaires being sent out and regular newsletters notifying participants when questionnaires have been sent. Nonresponders to the postal questionnaires will be sent a postcard reminder, an additional copy of the questionnaire, and if there is still not response we will attempt to collect a minimum dataset over the telephone. The baseline questionnaire will be administered by the research physiotherapists, and completed by the participant. We will send follow-up postal questionnaires at six weeks, six and twelve months. Nonresponders will be sent a reminder postcard and then an additional copy of the questionnaire. Persistent non-responders will be contacted by telephone in order to collect a minimum dataset. Two weeks after the twelve month questionnaire is sent, all participants will be contacted by telephone. As well as collecting a minimum dataset from non-responders, it will allow a brief semi-structured interview asking all participants about their overall experience of the trial and subsequent follow-up treatment. Blinding to treatment allocation will be maintained during these telephone interviews. Once again, in order to assess whether blinding has been maintained participants will also be asked to complete a five point Likert scale concerning which treatment group they believed that they were in.

7. Assessment of Safety

The procedures regarding safety monitoring, pharmacovigilance and urgent safety measures will be as described in NWORTH SOPs 4.03 and 4.06. As part of site initiation, training will include an overview of possible side effects/potential adverse reactions associated with adalimumab.

7.1 Recording Adverse Events and Adverse Reactions

All trial staff and clinicians in contact with trial participants will be responsible for noting adverse events that are reported by the participant and making them known to appropriate medical staff. Trial participants will be encouraged from the outset of the trial to contact the research team at the time of an event occurring. Participants will be given a leaflet or card containing a contact address and telephone number which they will be encouraged to contact should they experience any adverse event. All adverse events including non-serious adverse events will be recorded in the participant's medical records and the participant's Case Report Form. All adverse events as defined should be reported up to 1 month from the conclusion of all physiotherapy defined intervention. Adverse events will include:

- An exacerbation of a pre-existing illness.
- An increase in frequency or intensity of a pre-existing episodic condition.
- A condition (even though it may have been present prior to the start of the trial) detected after trial drug administration.
- Continuous persistent disease or symptoms present at baseline that worsens following the administration of the trial treatment.

The following will not be included as adverse events:

- Medical or surgical procedures -where the condition which leads to the procedure is the adverse event.
- Pre-existing disease or conditions present before treatment that do not worsen.
- Overdose of medication without signs or symptoms.

Known adverse reactions to adalimumab recorded in the SMPC include:

Blood and lymphatic system disorders	
Lauconconia (including poutroponia and	Vary common
Leucopoenia (including neutropenia and agranulocytosis)	Very common
Anaemia	Very common
	-
Leucocytosis	Common
Thrombocytopenia	Common
	Common
Idiopathic thrombocytopenic purpura	Uncommon
Desertes esis	Dava
Pancytopenia	Rare
Cardiac disorder	
Tachycardia	Common
myocardial infarction	Uncommon
Arrhythmia	Uncommon
Conceptive heart failure	Lincommon
Congestive heart failure	Uncommon
Cardiac arrest	Rare
F 111 - 24 - 12 - 1	
Ear and labyrinth disorders	
Vertigo	Common
Deafness	Uncommon
Tinnitus	Uncommon
Eye disorders	
Visual impairment	Common
Conjunctivitis	Common
Blepharitis	Common
Eye swelling	Common
,	
Diplopia	Uncommon

Gastrointestinal disorders	
Abdominal pain	Very common
Nausea and vomiting	Very common
GI haemorrhage	Common
Dyspepsia,	Common
Gastroesophageal reflux disease	Common
Sicca syndrome	Common
Pancreatitis,	Uncommon
Dysphagia	Uncommon
Face oedema	Uncommon
Intestinal perforation	Rare
General disorders and administration site of	condition
Injection site reaction (including injection site erythema)	Very Common
Chest pain	Common
Oedema,	Common
Pyrexia	Common
Inflammation	Uncommon
Hepatobiliary disorders	
Elevated liver enzymes	Very Common
Cholecystitis and cholelithiasis,	Uncommon
Hepatic steatosis,	Uncommon
Bilirubin increased	Uncommon
Hepatitis	Rare
Reactivation of hepatitis	Rare
Autoimmune hepatitis	Rare
Liver failure	Not known

Immune system disorders	
Hypersensitivity	Common

Allergies (including seasonal allergy)	Common
Sarcoidosis	Uncommon
Anaphylaxis	Rare
Metabolism and nutrition disorders	
Lipids increased	Very common
Hypokalaemia	Common
Uric acid increased	Common
Blood sodium abnormal	Common
Hypocalcaemia	Common
Hyperglycaemia	Common
Hypophosphatemia,	Common
Dehydration	Common
Infections and infestations	
Respiratory tract infections (including lower and upper respiratory tract infection, pneumonia, sinusitis, pharyngitis, nasopharyngitis and pneumonia herpes viral)	Very common
Systemic infections (including sepsis, candidiasis and influenza)	Very common
Intestinal infections (including gastroenteritis viral)	Very common
Skin and soft tissue infections (including paronychia, cellulitis, impetigo, necrotising fasciitis and herpes zoster),	Common
Ear infections	Common
Oral infections (including herpes simplex, oral herpes and tooth infections),	Common
Reproductive tract infections (including vulvovaginal mycotic infection)	Common
Urinary tract infections (including pyelonephritis)	Common
Fungal infections	Common
Joint infections	Common

Neurological infections (including viral	Uncommon
meningitis)	
Opportunistic infections and tuberculosis	Uncommon
(including coccidioidomycosis,	
histoplasmosis and mycobacterium avium	
complex infection)	
Bacterial infections	Uncommon
Eve infections	
Eye infections	Uncommon
Diverticulitis	Uncommon
Injury, poisoning and procedural complicati	on
injury, polooning and procedural complication	
Impaired healing	Common
Investigations	
Coagulation and bleeding disorders	Common
Coagulation and bleeding disorders (including activated partial thromboplastin	Common
Coagulation and bleeding disorders	Common
Coagulation and bleeding disorders (including activated partial thromboplastin	Common
Coagulation and bleeding disorders (including activated partial thromboplastin time prolonged)	
Coagulation and bleeding disorders (including activated partial thromboplastin time prolonged) Autoantibody test positive (including double stranded DNA antibody)	Common
Coagulation and bleeding disorders (including activated partial thromboplastin time prolonged) Autoantibody test positive (including	
Coagulation and bleeding disorders (including activated partial thromboplastin time prolonged) Autoantibody test positive (including double stranded DNA antibody)	Common
Coagulation and bleeding disorders (including activated partial thromboplastin time prolonged) Autoantibody test positive (including double stranded DNA antibody) Blood lactate dehydrogenase increased Musculoskeletal and, connective tissue dis Musculoskeletal pain	Common
Coagulation and bleeding disorders (including activated partial thromboplastin time prolonged) Autoantibody test positive (including double stranded DNA antibody) Blood lactate dehydrogenase increased Musculoskeletal and, connective tissue dis Musculoskeletal pain Muscle spasms (including blood	Common Common orders
Coagulation and bleeding disorders (including activated partial thromboplastin time prolonged) Autoantibody test positive (including double stranded DNA antibody) Blood lactate dehydrogenase increased Musculoskeletal and, connective tissue dis Musculoskeletal pain Muscle spasms (including blood creatinine phosphokinase increased)	Common Common orders Very common Common
Coagulation and bleeding disorders (including activated partial thromboplastin time prolonged) Autoantibody test positive (including double stranded DNA antibody) Blood lactate dehydrogenase increased Musculoskeletal and, connective tissue dis Musculoskeletal pain Muscle spasms (including blood	Common Common orders Very common
Coagulation and bleeding disorders (including activated partial thromboplastin time prolonged) Autoantibody test positive (including double stranded DNA antibody) Blood lactate dehydrogenase increased Musculoskeletal and, connective tissue dis Musculoskeletal pain Muscle spasms (including blood creatinine phosphokinase increased)	Common Common orders Very common Common

Neoplasms benign, malignant and unspecified (incl cysts and polyps)		
Skin cancer excluding melanoma (including basal cell carcinoma and squamous cell carcinoma),	Common	
Benign neoplasm	Common	
Lymphoma	Uncommon	
Solid organ neoplasm (including breast cancer, lung neoplasm and thyroid neoplasm), melanoma	Uncommon	

Leukaemia	Rare
Hepatosplenic T-cell lymphoma	Not known
Merkel cell carcinoma (neuroendocrine carcinoma of the skin)	Not known
Nervous system disorders	
Headache	Very common
Paraesthesias (including hypoaesthesia)	Common
Migraine,	Common
Nerve root compression	Common
Cerebrovascular accident	Uncommon
Tremor	Uncommon
Neuropathy	Uncommon
Multiple sclerosis	Rare
Demyelinating disorders (e.g. optic neuritis, Guillain-Barré syndrome)	Rare
Psychiatric disorder	
Mood alterations (including depression)	Common
Anxiety	Common
Insomnia	Common

Renal and urinary disorder		
Renal impairment	Common	
Haematuria	Common	
Nocturia	Uncommon	
Reproductive system and breast disorders		
Erectile dysfunction	Uncommon	
Respiratory, thoracic and mediastinal disorder		
Asthma,	Common	
Dyspnoea,	Common	

Cough	Common
Pulmonary embolism	Uncommon
Interstitial lung disease	Uncommon
Chronic obstructive pulmonary disease	Uncommon
Pneumonitis	Uncommon
Pleural effusion	Uncommon
Pulmonary fibrosis	Rare
Skin and subcutaneous tissue disorders	
Rash (including exfoliative rash	Very Common
Worsening or new onset of psoriasis (including palmoplantar pustular psoriasis	Common
Urticaria	Common
Bruising (including purpura)	Common
Dermatitis (including eczema),	Common
Onychoclasis,	Common
Hyperhydrosis,	Common
Alopecia	Common
Pruritus	Common
Night sweats,	Uncommon
Scar	Uncommon
Erythema multiforme	Rare
Stevens-Johnson syndrome	Rare
Angioedema	Rare
Cutaneous vasculitis	Rare
Worsening of symptoms of	Not known
dermatomyositis	
Vascular disorders	
Hypertension	Common
Flushing	Common
Haematoma	Common
Aortic aneurysm	Uncommon
Vascular arterial occlusion	Uncommon

Thrombophlebitis	Uncommon

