4.3 Exclusion criteria

- Symptoms persisting for longer than six months (obtained by asking the participant)
- A previous episode of sciatica in the last six months
- Unable to perform MRI (e.g. magnetic metal implants, potential metallic intraocular foreign bodies, claustrophobia, extreme obesity) obtained from the medical records and by asking the participant
- Serious spinal pathology, including cauda equina syndrome, malignancy, recent fracture, infection or very large disc prolapse which might require an urgent spinal surgery opinion, identified from participants' previous medical history in their medical records or from magnetic resonance imaging (MRI)
- Incidental serious pathology identified by MRI (e.g. adrenal tumour)
- Neurological deficit involving muscle weakness requiring an urgent spinal surgery assessment e.g. foot drop
- Widespread pain throughout the body including the upper limb [35] (Pain is considered widespread when all of the following are present: pain in the left

side of the body, pain in the right side of the body, pain above the waist, and pain below the waist. In addition, axial skeletal pain (cervical spine or anterior chest or thoracic spine or low back) must be present).

- Prior use of biological agents targeting TNF-alpha within the previous six months obtained from the medical records and by asking participant;
- Previous lumbar spinal surgery obtained from the medical records and by asking the participant;
- Contra-indications to adalimumab injection including serious infection such as active or latent tuberculosis, transplanted organ, demyelinating disorders, malignancy, cardiac failure, low white cell count, pregnancy obtained from the medical records, results of investigations and by asking the participant;
- Pregnant or breast-feeding (women must not breastfeed for at least five months after the last adalimumab injection).
- Unable to communicate in English or Welsh.
- Unable or unwilling to give informed consent.

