4.4 Informed consent

At the initial physiotherapy clinic the research physiotherapist will determine preliminary eligibility and the nature of the trial will be explained and a repeat participant information sheet (PIS) given. The PIS will have been approved by the ethics committee and will set out all key information including: the practicalities of the trial, the possible benefits, risks, and trial assessments. Participants will be registered onto the trial and details will be recorded on a database and a screening log at each of the trial treatment sites and participants will be assigned a unique participant registration identification number. Anonymised details labelled with the unique participant registration identification number will be transferred to a separate database in NWORTH, which will be used for recording all of the trial data. This will ensure that outcome measurement and statistical analysis will be performed blind to treatment allocation. All databases will be password protected. The participant consent forms will be stored in a locked filing cabinet in each treatment site. Clinical findings will be recorded on case report forms.

Eligible participants who give initial consent will have blood tests to exclude haematological and biochemical abnormalities (FBC, U+E, eGFR, LFT, Hba1c). They

will receive tuberculosis (TB) screening including a plain chest radiograph, biological agents counselling and magnetic resonance imaging (MRI) to exclude serious spinal pathology within 2-3 weeks of their initial visit. When MRI has excluded serious spinal pathology, TB screening, pregnancy test for eligible women and biological agent counselling has been completed, participants will attend a further appointment with the research physiotherapist. A second clinical assessment will be performed and if they are still eligible a second informed consent form, approved by the ethics committee will be completed in order to enter the RCT, the participant will be randomised by the research physiotherapist using a remote web-based system (See section 4.9). A letter will be sent to the participant's GP by the treatment site to inform them that the participant is taking part in the trial and request that the GP make a note of this in the patient record. In addition GPs will be requested to inform the trial team if they become aware the participant has experienced an adverse event or serious adverse event during the trial. (See section 7.0).

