minutes each. The therapy sessions will be provided over a period of 12 weeks. The number of sessions provided will be determined by participant and therapist preference and also response to treatment. We will capture and describe these aspects of physiotherapy treatment as part of the trial. In our proposed pathway the physiotherapy treatment starts at the same time as the injection intervention in both arms of the trial. Participants will be discouraged from receiving any other NHS-based co-intervention until this physiotherapy treatment has finished.

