7.2 Recording Serious Adverse Events and Serious Adverse Reactions

The definition of a serious adverse event (SAE) will be any medical event that:

- Results in death.
- Is life-threatening [refers to an event during which the participant was at risk of death at the time of the event; it does not refer to an event which might have caused death had it been more severe in nature].
- Requires hospitalisation, or prolongation of existing hospitalisation.
- Results in persistent/significant disability or incapacity.
- Is a congenital abnormality or birth defect.
- Other important medical events that, based upon appropriate medical judgment, may jeopardise the participant and may require medical or surgical intervention.

All SAEs and Serious Adverse Reactions (SARs) will be recorded in the 'Investigator Site File and the NWORTH trial unit manager will be informed immediately. The principal investigator or chief investigator at the treatment site will scan and email details of the SAE or SAR to the NWORTH trial unit manager via the NWORTH Sciatic trial manager who will record the information on the trial master file. Following the initial report, all SAEs should be followed up to resolution wherever possible and further information may be requested by NWORTH. The participant will be identified only by the participant's identification number. The participant's name should not be used on any correspondence. Once an SAE is received at NWORTH, it will be evaluated by the CI (or his delegate) for seriousness, expectedness and causality. The causality and expectedness assessment given by the PI cannot be overruled by the CI (or his delegate) and in the case of disagreement; both opinions will be provided with the report.

All SAEs will be reported to the sponsor's representative in Bangor University within 24 hours of being discovered, oversight and pathways for adverse incident reporting during the trial period will be managed by the sponsor's representative within the Healthcare and Medical Sciences Academic Ethics Committee (HCMS AEC) reporting to a standing –committee for trials within the University Ethics Committee (UREC) on behalf of Council. On an annual basis a 'Development Safety Update Report' (DSUR) containing a list of all SAEs and SARs will be submitted to the

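### Adverse-event reporting ends one month after physiotherapy concludes, an undefined and participant-specific point that also conflicts with the six-month adverse-event collection in the schedule

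*Protocol*

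**What the plan says.** Four parts of the protocol bear on when adverse-event collection ends.

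- **Section 7.1** gives the reporting rule: "All adverse events as defined should be reported up to 1 month from the conclusion of all physiotherapy defined intervention".
- **Section 5.2** describes the physiotherapy to which the rule is tied: "The therapy sessions will be provided over a period of 12 weeks", and "The number of sessions provided will be determined by participant and therapist preference and also response to treatment". It also says that "the physiotherapy treatment starts at the same time as the injection intervention in both arms of the trial". Section 5.3 then treats completion of the course as a milestone reached by each participant, after which they are discharged or referred on.
- **The data collection schedule** that follows section 5.4 has a row headed "Adverse Events". Its ticks read as randomisation, both treatment visits, six weeks and six months, with none at 12 months.
- **Sections 4.4 and 7.2** carry no physiotherapy-based limit. GPs are asked to tell the trial team "if they become aware the participant has experienced an adverse event or serious adverse event during the trial". For serious events, "all SAEs should be followed up to resolution wherever possible", and no closing date for reporting is given.

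Section 2.1 lists adverse effects among the secondary outcomes, so a comparison between arms is intended.

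**The concern.** An observation window for safety should close at a time that treatment cannot influence. Here it closes one month after an event that occurs after randomisation, and that event is not defined. *Conclusion* could mean the last session a participant attends, or the end of the 12-week period in which sessions are available. Neither reading is stated, and the first gives no end date for someone who attends no session.

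Under the first reading, two participants with the same risk can be watched for different lengths of time. If the timing of the last session differs by arm, a crude comparison of the proportions with an event partly reflects observation time.

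The second problem does not depend on the reading. A site following 7.1 would stop recording non-serious events well before the six-month contact at which the schedule expects them. For an event at week 20, the schedule and 7.1 point in different directions. An analysis plan cannot recover events that sites never recorded.

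**Working it through.** **What can be checked.** The protocol gives no adverse-event rate, no distribution of physiotherapy end dates and no safety power, so there is no stated safety figure to reproduce. The arm size used below comes from section 8.1: 332 / 2 = 166. The section 8.1 calculation reproduces: 133 per arm gives power 0.9015 for an effect of 0.4 SD with a two-sided 5% t test, and 266 / 0.80 = 332.5.

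**Step 1: latest close of the 7.1 window.** One month = 52 / 12 = 4.33 weeks. With physiotherapy starting with the injection (section 5.2) and lasting at most 12 weeks, the window closes at 12 + 4.33 = week 16.3.

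**Step 2: against the schedule.** Six months = 52 / 2 = week 26, so the shortfall is 26 − 16.3 = 9.7 weeks. If physiotherapy began two weeks later, at the second injection, the close would be 16.3 + 2 = week 18.3, still before week 26. The conflict therefore holds under either reading of *conclusion*.

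**Step 3: does observation time differ by arm?**

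- *Conclusion = week 12 for everyone.* All participants have 16.3 weeks. With equal true hazards the apparent risk ratio is 1.00.
- *Conclusion = last session attended.* The result depends on who finishes early. The following inputs are assumptions, not protocol figures: responders finish at week r, all others at week 12; the true event hazard h is constant and equal in both arms; the risk over 16.3 weeks is 10% to 50%.

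Formulae, with p the proportion of responders in an arm:

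- h = −ln(1 − risk) / 16.33
- mean observation = p(r + 4.33) + (1 − p)(16.33)
- observed risk = p[1 − exp(−h(r + 4.33))] + (1 − p)[1 − exp(−16.33h)]

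Worked case: r = 6, response 50% v 30%, risk 30%. Then h = 0.3567 / 16.33 = 0.0218. A responder is observed for 10.33 weeks and has risk 1 − exp(−0.2257) = 0.202. Adalimumab: 0.5 × 0.202 + 0.5 × 0.300 = 0.251. Placebo: 0.3 × 0.202 + 0.7 × 0.300 = 0.271. Apparent risk ratio 0.93, with no true difference.

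| Responders finish | Response, adalimumab v placebo | Mean weeks observed | Apparent risk ratio | Fewer participants with an event on adalimumab (166 per arm) |
|---|---|---|---|---|
| Week 8 | 50% v 40% | 14.3 v 14.7 | 0.97 to 0.98 | 0.4 to 1.5 |
| Week 6 | 50% v 30% | 13.3 v 14.5 | 0.92 to 0.94 | 1.2 to 4.8 |
| Week 4 | 60% v 30% | 11.5 v 13.9 | 0.83 to 0.86 | 2.4 to 10.1 |
| Any | equal | equal | 1.00 | 0 |

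**Step 4: direction.** The table assumes that benefit ends physiotherapy early and is more common on adalimumab. Section 5.2 also names preference, so participants who gain nothing may stop attending early. Exchanging the arms turns the range 0.83 to 0.98 into 1 / 0.98 = 1.02 to 1 / 0.83 = 1.20.

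**Step 5: after the change.** With one fixed window the ratio of observation times is 1.00, and so is the apparent risk ratio under equal hazards.

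**The case against.** The strongest reply is that section 5.2 makes the *number* of sessions depend on response, not the length of the course. A responder may have fewer sessions spread over the same 12 weeks, in which case everyone is observed for about 16.3 weeks. The schedule's six-month collection, if carried out, already supplies a common window. The SAP, not available here, may use person-time or a fixed window.

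Much of this stands, and it rules out several stronger inferences.

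- A reader might infer that the safety comparison *is* biased in favour of adalimumab. The protocol does not establish that course length differs by arm or in which direction.
- A reader might infer a large distortion by supposing that one whole arm finishes early and the other at week 12. If all adalimumab participants and no placebo participants finished at week 4, the apparent risk ratio would be 0.52 to 0.60. Nothing in the protocol supports so complete a separation, and both arms are offered the same physiotherapy. Events clustered around the two injections would shrink the effect further.
- A reader might set the 7.1 window against the rule that "women must not breastfeed for at least five months after the last adalimumab injection" and conclude that it closes during relevant exposure. That rule, and the matching contraception rule, are reproductive precautions. The protocol does not present them as a period for observing adverse events.
- A reader might infer that late events are lost altogether, or that a serious-event question at 12 months is needed. The GP request and section 7.2 leave those routes open.

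The reply does not define *conclusion*, provide for someone who attends no session, or reconcile 7.1 with the six-month tick.

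**Conclusion.** The point holds as a contradiction and an avoidable weakness, not as a demonstrated bias. The 7.1 window, closing by about week 16.3, ends roughly 9.7 weeks before the six-month adverse-event collection in the schedule, and this is so under either reading. It also does not match the GP and serious-event routes, which have no such limit.

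Unequal observation between arms is possible only if *conclusion* means the last session attended and its timing differs by arm. Apparent risk ratios of about 0.83 to 0.98 illustrate the size if early finishing is commoner on adalimumab. They rest on assumed response rates, assumed finishing times and a constant hazard. The true size and direction are unknown, and the effect is nil if week 12 applies to all.

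One caveat: the tick positions were read from extracted text. The Oswestry and MRI-reporting rows fall where the protocol text places them, which supports the reading.

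**What to change.** Replace the cut-off in section 7.1 with one fixed calendar window, counted from first injection or randomisation, identical for every participant and independent of physiotherapy attendance. The six-month contact already in the schedule is a natural end point. Make section 7.1, the schedule, the GP request in section 4.4 and section 7.2 consistent with it, stating which window applies to all adverse events and that serious-event reporting is not limited by physiotherapy. Compare the arms on events within the common window.

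The cost is a wording amendment and some additional recording of non-serious events between about week 16 and the six-month contact. No new visits are needed.
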